2.3.2 KNOWN POTENTIAL BENEFITS

Potential benefits of mini-facelift surgery include improvement in visible signs of aging on the face (e.g., improvement in wrinkles and laxity) and improved self-esteem from a good cosmetic outcome.

Known potential benefits of the Omnilux new-U for LED-RL include reduction of periorbital wrinkles, the current FDA indication for use. The potential benefit of scar prevention is being studied in this protocol.

Patients with post-surgical scars and skin fibrosis in general have limited treatment options. Even with treatment, skin fibrosis often persists and recurrence rates are high. If LED-RL phototherapy is effective at preventing hypertrophic or keloidal periauricular scarring, subjects will benefit from improved scar appearance and symptomology. This benefit by patients will in turn aid medicine and science.

2.3.3 ASSESSMENT OF POTENTIAL RISKS AND BENEFITS

Although no surgical procedure is without complications, facelift surgery is considered to be a safe procedure with a low incidence of major complications, with hematoma (1.1%) and infection (0.3%) being the most common but still occur infrequently.³⁹ We chose mini-facelift incisions as the surgical wound model for the following reasons: it is considered to be a safe procedure, performed in-office with tumescent local anesthesia; it offers an aesthetic benefit to patients who are interested in facial rejuvenation; and the surgical incisions are made in relatively inconspicuous areas near the earlobes and are symmetrical, allowing for a split-face study. We believe that given the low incidence of complications of this commonly performed elective cosmetic procedure, combined with the fact that the procedure in this protocol is a minimal incision facelift (as opposed to the traditional full facelift that requires more extensive incisions and longer recovery time), the value of information to be gained by studying this surgical wound model outweighs the risks involved.

LED-RL phototherapy is also considered to be a safe procedure that is done routinely in outpatient clinics and even at home. We will monitor for any unforeseen adverse events caused by LED-RL and follow study stopping rules, as described below. LED-RL phototherapy is completely non-invasive, does not cause thermal or chemical damage, and does not have post-procedure down time. The risk of side effects is minimal and those that do occur are usually transient and minor (e.g., mild erythema lasting less than 24 hours). We believe that the value of the information to be gained in this study outweighs the potential risks involved in LED-RL phototherapy, given that the treatment device is FDA-cleared for over-the-counter use on the face and has been clinically proven to be safe and well tolerated at the proposed treatment doses.

The skin biopsies are optional and will be used for research purposes only. Minimal risk of scar will be incurred by subjects undergoing biopsy, as a 2 mm punch biopsy tool (the smallest sized instrument that can be used to obtain useful histological and molecular analysis) was selected to minimize

discomfort and reduce the risk of scarring. The 2 mm size is so small that the punch biopsy defect (skin wound) does not require suturing and heals by secondary intention.

During the study, subjects are asked to refrain from using scar treatments to both periauricular incision sites, as to not confound the results of the study. They will be counseled on standard postoperative care of the incisions to optimize wound healing. Subjects are allowed to seek scar treatment, if desired, at the conclusion of the study (i.e., after the final study visit at 6 months postsurgery). Facial skin is known to heal well, and thus have lower risk of abnormal scarring, compared to other body sites due to its rich vasculature and low tensile forces.^{40,41} Since most cutaneous injuries (such as surgical incisions) heal with a normotrophic scar over time,^{41,42} the study's requirement that subjects wait 6 months post-surgery to seek scar treatment is not expected to cause irreversible health problems or extreme suffering. A normotrophic scar is defined as a flesh-colored, flat scar (as opposed to hypertrophic scars or keloids, pathological scars that are elevated and can be symptomatic).^{42,43} Furthermore, the remodeling phase of skin wound healing can take over a year, meaning that the scar maturation process is lengthy and the final scar appearance may not be known until 6 months to 2 years after surgery.^{44,45} It is important to note that should pathological scarring develop in a subject, it will not be evident until several months post-surgery, as this is the general timepoint at which a hyperplastic response (i.e., abnormal scar tissue formation) is observed.⁴¹ In clinical practice, it is recommended that hypertrophic scars be allowed the opportunity to regress on their own before initiating aggressive anti-scarring treaments such as scar revision surgery.^{43,46}

Stopping Rules: Subjects will have the ability to leave the study at any time without penalty for discontinuation of participation. Adverse events, serious adverse events, and unanticipated problems (as described in *Section 8: Study Assessments and Procedures*) will be monitored and the trial will be halted early if necessary to protect subjects. Any life threatening events and/or deaths (grade 4 and 5 toxicity) attributable to the study protocol will result in halting the study. Toxicity data and adverse events will be monitored by the PI and the IRB.

3 OBJECTIVES AND ENDPOINTS

OBJECTIVES	ENDPOINTS	JUSTIFICATION FOR ENDPOINTS
Primary		
To evaluate the	The difference in quantitative scar pliability	Various objective scar assessment tools are
clinical efficacy of LED-	between the LED-RL treated and control	available to assess biomechanical
RL phototherapy in	incision sites	properties of the skin, including pliability,
the prevention of skin		which correlates with degree of skin
fibrosis in subjects	Skin elasticity (stiffness) and induration, which	fibrosis. ^{47–52} These devices have shown less
undergoing elective	reflect scar pliability, are objectively quantified	pliability in scars as compared to normal
mini-facelift surgery	with two different indentation instruments, the	controls and are commonly used to
	ElastiMeter and the SkinFibroMeter. These	measure the efficacy of scar treatments. ⁵³
	non-invasive handheld tools measure vertical	The ElastiMeter demonstrates accuracy and
	deformation on the skin surface; the indenter is	reliability to assess skin elasticity. ⁵⁴ The
	pressed quickly onto the skin and the sensors	SkinFibroMeter has good reliability
	measure the force resisting the strain. Scar	compared with other elasticity
	tissue is less supple than normal skin due to	measurement devices and has been applied
	scar thickness and inferior quality of collagen	in clinical studies to assess skin fibrosis.55,56

OBJECTIVES	ENDPOINTS	JUSTIFICATION FOR ENDPOINTS
	architecture. Elasticity and induration measurements are performed prior to treatment and at follow-up visits on POD 30, 90, and 180.	
Secondary		
To evaluate the histological, ultrastructural, and molecular changes that occur in vivo as a result of LED-RL phototherapy	Histological and molecular analyses of treated and control skin specimens Skin samples from LED-treated and mock- treated incision sites are obtained for histology and molecular studies. Tissue specimens from POD 30 (post-treatment) are compared to those from POD 0 (pre-treatment). Histological examination includes quantification of Ki-67 positive fibroblasts and qualitative assessment of collagen. Molecular testing includes RNA- Seq, microRNA arrays, and quantitative real- time PCR (qRT-PCR).	Non-invasive tests to evaluate cellular features of skin fibrosis are limited. Our in vitro data showed that high fluence LED-RL decreases fibroblast cell counts in keloid scar-derived fibroblast cultures ⁴ and that LED-RL modulates the PI3K/AKT pathway. ⁵⁷ To determine the mechanism associated with LED-RL anti-fibrotic effects in vivo , biopsies of the dermis (where skin fibrosis occurs) are needed to conduct histological examination and molecular studies.
To assess for clinically meaningful changes in scar characteristics after LED-RL phototherapy	Difference in the Patient and Observer Scar Assessment Scale (POSAS) scores between the treated and control incision sites Subjective scar evaluation is performed using the POSAS, a standardized and validated tool to assess scar quality. ^{58–60} The observer scar assessments are completed in-clinic by a blinded investigator in conjunction with subject assessments at multiple time points (follow-up visits on POD 30, 90, and 180). Each parameter on the POSAS is scored from 1 to 10, where 1 is "normal skin" and 10 is the "worst imaginable scar".	The POSAS is the most frequently used scar assessment scale for post-surgical scars ⁶¹ and is often used as a primary outcome measure for treatment efficacy in clinical trials. The POSAS was devised to quantify scar appearance in response to treatment and demonstrates internal consistency, inter-observer reliability, and agreement. ^{53,58} Importantly, the POSAS incorporates the patient's judgment of scar appearance and includes subjective symptoms of pain and pruritus, allowing for a more comprehensive evaluation in comparison to an evaluation by clinicians alone.
	Difference in the photograph-based Visual Analogue Scale (VAS) scores between the treated and control incision sites An independent panel of two blinded dermatologists will evaluate standardized split- face scar photographs, using a validated VAS scoring and ranking system. ^{53,62,63} Each scar dimension is rated on a 10 cm VAS such that	The VAS has demonstrated high observer reliability and internal consistency in expert panel evaluations. ^{53,63} The VAS has been used in various scar trials ⁵³ and Duncan et al. showed that the VAS scar scoring and scar ranking methods are consistent, reliable, valid, and feasible for assessing linear scars. ⁶²

OBJECTIVES	ENDPOINTS	JUSTIFICATION FOR ENDPOINTS
	higher numerical scores correlated with more	
	severe scars.	
	Difference in objective measurements of key	OCT has been used to non-invasively
	scar characteristics between the treated and	evaluate skin fibrosis at high resolution
	control incision sites	without discernible effect on tissue. ⁶⁵ This
		imaging technique is highly suited to
	A diverse set of novel, non-invasive skin	fibrosis assessment and may represent a
	analysis tools will be used to objectively	diagnostic alternative to punch biopsies. ⁶⁶
	measure key scar characteristics: collagen and	
	water concentration, wrinkles, texture,	Three-dimensional skin imaging analysis
	diameter, area, volume of elevation, pores,	provides quantitative measurements of
	pigmentation, and vascularity. The VivoSight	various scar tissue indicators such as
	uses multi-beam OCT technology to provide	pigmentation, vascularity, texture, and
	high-resolution cross-sectional images and	volume of depressions and elevations.
	measure scar depth, collagen density, and	Because it is an objective analysis tool, it
	surface roughness. ⁶⁴ The Dermo is a	provides quantitative evidence of
	spectroscopy probe that measures collagen and	therapeutic results, avoiding the influence
	water concentration in the dermis. The Antera	of subjective evaluation that most scar
	3D camera and Cherry3 camera use multi-	assessments are based on. ^{67–69} It has been
	directional illumination to reconstruct three-	used to assess therapeutic efficacy of
	dimensional images of the skin surface for	various interventions on keloids and burn
	instant topographic and colorimetric analyses.	scars.
	These objective efficacy assessments will be	
	done prior to treatment initiation and at	
	follow-up visits.	
To continue to assess	The safety profile is determined by the	While two phase I studies demonstrated
the safety of LED-RL	incidence of common expected post-treatment	the safety of LED-RL in healthy subjects, the
, phototherapy on	effects, adverse events, serious adverse events,	safety of LED-RL in a mini-facelift surgical
human skin	and unanticipated problems throughout the	wound model may differ from the safety on
	study. Special attention will be paid to the	normal human skin. In addition, differential
	identification of any differential safety findings	safety effects of LED-RL on different skin
	based upon skin type (i.e., race and ethnicity),	types have not been described previously,
	given the findings of our previous Phase I trials.	but our previous research suggest that
		darker skin types may be more
		photosensitive to LED-RL.

4 STUDY DESIGN

4.1 OVERALL DESIGN

This is a Phase II clinical trial, following two previous Phase I studies of LED-RL on human skin in healthy subjects (STARS 1 and STARS 2). We will conduct a dose-ranging, randomized, parallel group, split-face, single-blind, mock-controlled study of LED-RL in eligible subjects who have decided to

undergo elective minimal incision facelift (i.e., mini-facelift) surgery. We hypothesize that LED-RL phototherapy may be a safe, well tolerated, and effective treatment for skin fibrosis.

The trial will be conducted at a single site: the Laser, Aesthetics and Body (LAB) Institute at SUNY Downstate Medical Center. The LAB Institute is part of the Center for Photomedicine, Department of Dermatology, and is located at University Hospital of Brooklyn. The mini-facelift surgery is a simple excision of redundant skin (i.e., excess lax facial skin) with wound closure. The surgery is done in-office in a procedure room within the LAB Institute, which is equipped with LED surgical lighting and stocked with standard care supplies, medications, and surgical instruments needed for dermatologic surgical procedures done in an ambulatory setting. The surgery is performed under tumescent local anesthesia by a board-certified dermatologic surgeon ([name]) at the baseline visit, referred to as postoperative day (POD) 0. Following the mini-facelift surgery, subjects will be counseled on standard postoperative wound care and be provided with a handout of instructions. Subjects are asked to adhere to the postoperative care instructions to optimize skin wound healing and to refrain from using scar treatments at the incision sites during the study.

The treatment side (right face versus left face) will also be randomized to control for effects of uneven sun exposure. The untreated side will receive mock therapy with sham irradiation via a mock device that looks, sounds, and feels similar to the treatment device, but does not produce light. Subjects will

be blinded to the LED-RL device versus mock device as the treatment site is outside of their range of view and they will wear safety goggles.

Beginning scar reduction therapy at 1 week after surgery (defined as POD 4 to POD 8) is a validated intervention time point for limiting surgical scars.¹ Subjects will receive their treatment sessions inoffice three times weekly, a standard phototherapy regimen,^{73–75} starting at 1 week post-surgery for a total of nine treatment sessions. This treatment schedule (frequency and duration) is identical to the schedules used in our Phase I studies. Each treatment session will be observed by an investigator to monitor for any adverse events and to ensure safety and adherence.

During the study, subjects will be asked to avoid scar treatments to both periauricular incision sites. Scar treatment options include, but are not limited to, silicone gels/sheets, intralesional corticosteroids, 5-fluorouracil, laser therapy, radiotherapy, cryotherapy, bleomycin, mitomycin C, imiquimod, pressure therapy, adhesive microporous hypoallergenic paper tape, onion extract, massage therapy, over-the-counter topical emollients for scars, laser therapy, and surgical revision.⁷⁶ As described above, subjects will be counseled on proper wound care during the postoperative period to facilitate appropriate wound healing. Refer to *Section 10.2: Additional Considerations* for a discussion of available scar treatments at the conclusion of the study.

Following the study intervention period, subjects will have follow-up assessments on approximately POD 30, 90, and 180. At each follow-up visit, scar characteristics will be recorded objectively and subjectively through skin elasticity and induration measurements, tissue histology, photographic evaluation, skin imaging analysis, collagen and water concentration measurements, OCT, and standardized patient and observer assessments as described in *Section 3: Objectives and Endpoints* and *Section 8: Study Assessments and Procedures*.

Skin specimens will be obtained via elective 2 mm punch biopsy on POD 0 (prior to surgery) and POD 30 (first follow-up visit after completion of LED-RL treatment). Skin specimens will be used for histological examination and molecular studies via RNA sequencing, microRNA analysis, and qRT-PCR.

4.2 SCIENTIFIC RATIONALE FOR STUDY DESIGN

The methodology of a dose-ranging, randomized, parallel group, split-face, single-blind, mock-controlled study offers several advantages.

A dose-ranging study design is implemented as the safety of LED-RL phototherapy in a surgical wound model may differ from the safety in normal skin. For example, higher fluences determined to be safe in normal skin may potentially cause problems in post-surgical/scarred skin, such as dehiscence. Thus, the MTD established in our Phase I studies serves as the upper limit of treatment dose in this study.

The split-face study design allows each subject to serve as his or her own control, allowing for a within-subject comparison of clinical efficacy between the treated side and mock-treated side. That is, any observed improvements in scar characteristics can be attributed to the treatment. The split-face design also eliminates the need to consider inter-individual differences in wound healing as a confounding factor when comparing different treatment arms. It is important to note that in the prospective evaluation of scar reduction therapy, it is assumed that if left untreated, the wounds on the treated side and untreated side would heal with identical scars. Since wound healing and scar

formation are influenced by many variables, the selection of a self-controlled study design is favored to allow detection of true treatment effects.

There are no known problems associated with the control (sham irradiation), since the mock device is designed to simulate the treatment device without actually producing light.

The mini-facelift with periauricular incisions is an ideal model for studying wound healing and skin fibrosis because: patients are motivated to have the best wound healing outcomes and aesthetic results (i.e., minimal or imperceptible scarring), hence will likely be compliant with therapy and have a low attrition rate; patients are usually healthy in order to be suitable candidates for the surgery; and the periauricular skin is at risk of pathological scar development, yet has low skin tension and robust blood circulation to allow for optimal wound healing.

4.4 END OF STUDY DEFINITION

A participant is considered to have completed the study if he or she has completed all phases of the study including the last visit shown in *Section 1.3, Schedule of Activities (SOA)*.

The end of the study is defined as completion of the last visit or procedure shown in the SOA in the trial globally. The end of the study is the point at which all required data has been collected to answer the research questions in the protocol.

5 STUDY POPULATION

5.1 INCLUSION CRITERIA

Individuals of any sex, ethnicity, and age may potentially be eligible to participate in this study. In order to be eligible to participate in this study, an individual must meet all of the following criteria:

- 1. Provision of signed and dated informed consent form
- 2. Stated willingness to comply with all study procedures and availability for the duration of the study
- 3. Desire to undergo elective mini-facelift surgery and is a suitable surgical candidate, as determined by the surgeon's clinical assessment
- 4. Pass a screening photosensitivity test

5.2 EXCLUSION CRITERIA

An individual who meets any of the following criteria will be excluded from participation in this study:

- 1. Concomitant use of any photosensitizing medications (e.g., lithium, melatonin, phenothiazine antipsychotics, tetracycline antibiotics, quinolone derivative antibiotics)⁺
- 2. Light-sensitive conditions
- 3. Diabetes mellitus
- 4. Systemic lupus erythematosus
- 5. Current tobacco use
- 6. History of bleeding or coagulation disorder
- 7. Lax skin associated with genetic disorders (e.g., Ehlers-Danlos, cutis laxa)
- 8. Open wounds on the face or neck
- 9. Fibrotic skin disease, pre-existing scar(s), or other skin conditions affecting the periauricular skin
- 10. History of surgery or procedure involving or affecting the periauricular facial skin within the past 6 months (e.g., facial plastic surgery, dermal fillers, physician-strength chemical peels, neuromodulator treatment, laser skin resurfacing), or plan to have such procedures during the study period
- 11. Tattoos that cover the proposed treatment sites on the periauricular skin
- 12. Any other medical condition(s) that could be compromised by exposure to the proposed treatment

⁺ Refer to *Section 6.5: Concomitant Therapy* for the full list of prohibited medications to be reviewed on case report forms.

5.3 LIFESTYLE CONSIDERATIONS

During this study, participants are asked to:

- Abstain from smoking
- Refrain from use of any scar treatments (e.g., silicone gel/sheets, intralesional corticosteroids, massage therapy, topical emollients, laser therapy, surgical revision) on the periauricular incision sites
- Avoid any elective cosmetic procedure that would affect the facial skin

If a prohibited medications, treatments, or procedures are indicated for standard of care, the participant will be withdrawn early from the study. Exceptions include, but are not limited to, use of a photosensitizing medication after the conclusion of the intervention period (i.e., after all LED-RL phototherapy sessions are completed).

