7 STUDY INTERVENTION DISCONTINUATION AND PARTICIPANT DISCONTINUATION/WITHDRAWAL

7.1 DISCONTINUATION OF STUDY INTERVENTION

Discontinuation from LED-RL phototherapy does not mean discontinuation from the study, and remaining study procedures should be completed as indicated by the study protocol. If a clinically significant finding is identified (including, but not limited to changes from baseline) after enrollment, the investigator or qualified designee will determine if any change in participant management is needed. Any new clinically relevant finding will be reported as an adverse event (AE).

The data to be collected at the time of study intervention discontinuation will include the following:

- Details of any adverse events (e.g., nature, severity, relationship to study intervention, and expectedness) will be documented in the CRFs
- Digital photography of the affected site(s), if applicable

Stopping Rules: Adverse events, serious adverse events, and unanticipated problems (as described in *Section 8: Study Assessments and Procedures*) will be monitored and the trial will be halted early if necessary to protect subjects. Any life threatening events and/or deaths (grade 4 and 5 toxicity) attributable to the study protocol will result in halting the study.

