7.2 PARTICIPANT DISCONTINUATION/WITHDRAWAL FROM THE STUDY

Participants are free to withdraw from participation in the study at any time upon request, without penalty. For example, the participant may withdraw after receiving the mini-facelift surgery but before starting treatment without being penalized for the procedure-related costs of the mini-facelift surgery.

An investigator may discontinue or withdraw a participant from the study for the following reasons:

- Significant study intervention non-compliance
- Any clinical adverse event (e.g., second-degree or higher skin burning, blistering, swelling, pain, ulceration, change in sensation, muscle weakness, worsening of surgical scar) or other medical condition or situation occurs such that continued participation in the study would not be in the best interest of the participant
- The participant meets an exclusion criterion (either newly developed or not previously recognized) that precludes further study participation
- Unforeseen serious adverse event (e.g., neurological symptoms lasting more than 24 hours) occurs

The reason for participant discontinuation or withdrawal from the study will be recorded on the CRF. Subjects who sign the informed consent form and are randomized but do not receive the study intervention may be replaced. Subjects who sign the informed consent form, and are randomized and receive the study intervention, and subsequently withdraw, or are withdrawn or discontinued from the study, will be replaced only if the enrollment period is still open.

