9.2 SAMPLE SIZE DETERMINATION

The study will have three treatment arms (LED-RL 160 J/cm², LED-RL 320 J/cm², and LED-RL 480 J/cm²) with 10 subjects each. The primary outcome measure is the difference in pliability between a treated incision site and the contralateral mock-treated incision site.

To calculate the sample size for this study, we anticipate that the minimal clinically important difference in scar pliability is 15%, based on minimum decrease in fibroblast cell number after LED-RL treatment from our *in vitro* data. A power analysis plan predicted that with 9 subjects, the study would have greater than 80% power to detect a 15% difference in pliability by using a two-sided paired *t*-test. To take into account a dropout rate of 10%, 10 subjects will be enrolled in each treatment arm. Up to 150 potential participants will be screened and a total of 30 subjects will be enrolled in the study.

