9.3 POPULATIONS FOR ANALYSES

- Intention-to-treat (ITT) analysis dataset: all participants who are enrolled and randomly allocated to treatment, regardless of treatment actually receive
- Per-protocol analysis dataset: participants who adhered to the protocol and completed the treatment originally allocated (i.e., attended all treatment sessions)
- Safety analysis dataset: participants who received at least one dose of the study intervention

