9.4.1 GENERAL APPROACH

In initial intention-to-treat analyses, all available data will be included. Multiple imputation will be used where dependent variable values are missing. In subsequent per-protocol analyses, only subjects with complete data will be included.

SAS (SAS Institute, Cary NC) 9.4 statistical software will be used.

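### Withdrawal tied to scar treatment or scar worsening can end pliability follow-up for reasons related to the primary outcome, and the plan has no sensitivity analysis for that loss

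*Combined protocol and SAP*

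**What the plan says.** Section 5.3 asks participants not to use any scar treatment on the incision sites. It then states a mandatory rule: "If a prohibited medications, treatments, or procedures are indicated for standard of care, the participant will be withdrawn early from the study". The list of exceptions is open, and the only one named is photosensitizing medication after the last phototherapy session.

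Section 7.2 lists grounds on which an investigator may withdraw a participant. One is a clinical adverse event, with examples that include "change in sensation, muscle weakness, worsening of surgical scar) or other medical condition or situation occurs", qualified by the participant's best interest. The same section allows subjects who were treated and then withdrawn to be replaced while enrollment is open.

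Section 7.1 says: "Discontinuation from LED-RL phototherapy does not mean discontinuation from the study", and that remaining procedures should be completed. It does not address withdrawal from the study.

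On the analysis side, 9.2 states: "The primary outcome measure is the difference in pliability between a treated incision site and the contralateral mock-treated incision site". Sections 3 and 9.1 place the readings before treatment and at POD 30, 90 and 180. The ITT set in 9.3 is "all participants who are enrolled and randomly allocated to treatment, regardless of treatment actually receive". Section 9.4.1 includes all available data and adds: "Multiple imputation will be used where dependent variable values are missing". It states no missingness assumption and no sensitivity analysis.

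**The concern.** A scar that becomes firm or raised is the event most likely to prompt scar treatment or to count as worsening. It is also what the ElastiMeter and SkinFibroMeter are there to detect. If such a subject leaves the study, the remaining readings are lost for a reason connected with their likely values. Because the comparison is within the face, one withdrawal removes both sides of the pair.

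Section 2.3.3 says pathological scarring shows only after several months, so the POD 90 and POD 180 readings are the ones most exposed. If the mock side is the bad scar, losing the pair hides benefit. If the LED-RL side is the bad scar, it hides harm. Imputation can draw on readings taken before withdrawal, but it cannot correct loss that depends on values never observed. With 10 subjects per arm there is little room to absorb this.

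**Working it through.** **1. The plan's own figure.** Section 9.2 states that "with 9 subjects, the study would have greater than 80% power to detect a 15% difference in pliability by using a two-sided paired" t-test, then allows 10% dropout. The dropout step reproduces: 9 / (1 − 0.10) = 10 per arm, 30 in total. The power statement cannot be checked, because neither the SD of the paired difference nor alpha is given.

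**2. Largest SD consistent with that statement.** Assume two-sided alpha 0.05. The exact noncentral-t calculation for 9 pairs needs a standardised difference of 1.067 for 80% power, so the SD is at most 15 / 1.067 = 14.06 points, reading the 15% as 15 points on a scale where the mock mean is 100. At that SD, power is 85%, 80% and 74% with 10, 9 and 8 evaluable subjects in an arm.

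**3. Margin for loss.** Assume each subject is lost independently with probability 0.10.
- Chance of at least two losses among 10: 1 − 0.9^10 − 10 × 0.1 × 0.9^9 = 1 − 0.349 − 0.387 = 0.26.
- Chance that this happens in at least one of three arms: 1 − (1 − 0.26)^3 = 0.60.

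These powers are for the paired t-test of 9.2. The mixed model of 9.4.2 pools arms and visits, so they are a guide only.

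**4. Selection when either scar can trigger withdrawal.** Simulated pairs have mock mean 100, treated mean 85 (higher is firmer) and between-side correlation r. The per-side SD is s = 14.06 / √(2(1 − r)), that is 11.88, 14.06 and 18.15 for r = 0.3, 0.5 and 0.7. A subject is withdrawn if either side exceeds the value that marks the worst 10% of mock scars.

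| r | Withdrawn | Completers' difference (true 15) | Shift |
|---|---|---|---|
| 0.3 | 10.3% | 13.5 | −1.5 |
| 0.5 | 10.5% | 13.8 | −1.2 |
| 0.7 | 10.4% | 14.1 | −0.9 |

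The shift is 6% to 10% of the 15 points (0.9 / 15 to 1.5 / 15). With a true difference of 0, the completers' difference stays at 0 within simulation error, because the rule treats the two sides alike.

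**5. Selection when only one side triggers withdrawal.** If the worst 10% on one side leave, that side's mean among those who stay falls by φ(1.2816) / 0.9 × s = 0.1755 / 0.9 × s = 0.195s, and the other side's falls by r times that. The difference therefore shifts by 0.195 × s × (1 − r):
- r = 0.3: 0.195 × 11.88 × 0.7 = 1.6
- r = 0.5: 0.195 × 14.06 × 0.5 = 1.4
- r = 0.7: 0.195 × 18.15 × 0.3 = 1.1

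Under a true null this appears in favour of LED-RL if the treated side drives withdrawal, and against it if the mock side does.

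**6. Direction under harm.** With a true difference of −15, the rule of step 4 at r = 0.5 leaves −11.3 in completers, so part of the harm is hidden. It would also withdraw 44% of subjects, so this shows direction and not a plausible size.

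Steps 4 to 6 are complete-case figures. Imputation from earlier readings could recover part of the shift.

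**The case against.** The strongest reply is that the triggers may seldom operate before POD 180. Section 10.2 treats scar treatment as cosmetic and elective, prefers to delay revision procedures to six months or later, and offers every subject cost-covered laser treatment after the final visit. Section 2.3.3 says hypertrophic scars should first be given time to regress. This stands: the frequency is unknown, and the loss rates above are assumptions.

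A reader might also infer several stronger things that the documents do not support.
- **That every subject whose scar worsens is removed.** Section 7.2 is discretionary and tied to best interest. Only 5.3 is mandatory, and its exceptions are open.
- **That 7.1 is contradicted.** It covers stopping phototherapy, whereas 5.3 and 7.2 cover leaving the study. There is tension only where the same event during the treatment weeks could follow either route.
- **That the ITT set is contradicted.** Withdrawn subjects stay in it. What is missing is data, not membership.
- **That imputation must fail.** If withdrawal follows a bad scar already measured at an earlier visit, the loss depends on observed data and imputation can use it.
- **That replacements heal better.** They come from the same population, and only while enrollment is open.
- **That the bias is about 2.7 points.** Trimming the 10% most extreme differences in one direction gives 0.195 × 14.06 = 2.7, or 18% of 15. That is a different mechanism from withdrawal for a bad scar on either side, which gives 0.9 to 1.5.

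Finally, readings taken after scar treatment are themselves affected by it, which is why the protocol prohibits it. That is a fair point about how to analyse those readings. It is no reason not to collect them.

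**Conclusion.** The point holds in limited form. One mandatory rule and one discretionary rule can end pliability follow-up because of the condition that the primary outcome measures. No later readings are provided for, and the missing-data plan does not examine outcome-dependent loss.

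The likely effect is modest. At about 10% loss triggered by either side, a true difference of 15 appears as about 13.5 to 14.1 in completers, with no bias under the null. If withdrawal follows one side only, the shift is about 1.1 to 1.6 points and can arise under the null. These sizes rest on assumed alpha, SD, correlation and loss rate, and on complete cases. The change is worth making because readings not taken cannot be recovered and the remedy is cheap.

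**What to change.** - Reword 5.3 and 7.2 so that receiving a prohibited scar treatment, or a worsening scar, does not by itself end outcome follow-up, whatever care is decided. Reconcile both with 7.1, so that stopping phototherapy, receiving scar treatment and leaving follow-up are three separate events.
- With the participant's consent, keep both-side pliability readings at the already scheduled Visits 11 to 13. Record the date, product and side of any scar treatment.
- In 9.4.1 and 9.4.2, state the missingness assumption behind the imputation. Analyse the primary outcome both with post-scar-treatment readings included and with them set to missing, and say in advance which is the main analysis.
- Add a missing-not-at-random sensitivity analysis, for example a delta adjustment to the imputed values.

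The cost is protocol wording and slightly more analysis work, with no new visits. The drawback is that some later readings will be affected by scar treatment, which the paired analyses make visible.
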